## **ABBREVIATIONS**

ASA-American Society of Anaesthesiologists

BP-Blood pressure

CAM-Confusion assessment method

CBF- Cerebral blood flow

CDT-Clock drawing test

CMR- Cerebral metabolic rate

CMRO2.Cerebral metabolic rate of Oxygen consumption

CNS-Central nervpus system

GA-General anaesthesia

GCS- Glasgow Coma Scale

Hb-Hemoglobin

MAC-Mean alveolar concentration

MMSE-Mini mental state examination

NMT-Neuromuscular transmission

NRS-Numerical rating score

POD-Post operative delirium

## INTRODUCTION

In simple words delirium is defined as a temporary state of confusion . It is characterized by acute onset, fluctuating course, inattention, disorganized thinking, altered level of consciousness, perceptual disturbances, psychomotor disturbances, altered sleep-wake cycle, and emotional disturbances. Postoperative delirium (POD ) is disturbance of consciousness seen 24 to 72 hours after surgery. Its incidence varies from 5% to 15% but in high-risk groups such as cardiac and orthopedic patients, the range is 16–62%. Postoperative delirium is not only distressing for patient but also for family members. It is associated with functional decline, need for prolonged nursing care and prevent functional recovery. Hence it leads to prolonged duration of hospital stay and adds to morbidity and mortality in the long term. Exact mechanism responsible for POD is not known but several risk factors are found to be associated with POD. This includes patient related, surgery related and anesthesia related factors.

The incidence of POD in spine surgery in previous studies was found to be between 3.3% to 3.8%. Spine surgeries are associated with significant postoperative pain, blood loss, long duration of surgery and all these factors may be associated with POD after spine surgeries. But for the smooth conduct of spine surgery general anesthesia (GA) is required. During general anesthesia either inhalational volatile agents or intravenous hypnotic agents are used. However effect of the type of anesthetic agents in spine surgeries on postoperative delirium have not been studied previously. Both isoflurane and desflurane are commonly used inhalational agents. Now a days many centers prefer to use desflurane over isoflurane due to its low blood gas solubility which results in faster emergence. Among the inhalational volatile agents, previous studies have

compared the incidence of postoperative delirium with sevoflurane and desflurane especially in children and elderly individuals. But no study has compared the incidence of postoperative delirium with isoflurane and desflurane in middle aged adults undergoing spine surgery .

Desflurane is associated with faster emergence and lesser incidence of postoperative cognitive dysfunction compared to isoflurane. Animal studies have shown that prolonged exposure to isoflurane to be neurotoxic. We hypothesize that the adverse neurological outcomes associated with isoflurane compared to desflurane may be associated with an increased incidence of postoperative delirium. Hence we are conducting this study to compare the occurrence of postoperative delirium with Isoflurane and Desflurane in spine surgery patients.

## **REVIEW OF LITERATURE**

Brain functions are known to be affected during immediate postoperative period after exposure to anesthesia. These effects vary from depressed levels of consciousness with impairment of attention and memory to complete amnesia for several hours. Cognitive disturbances commonly seen in postoperative period are delirium and cognitive disturbances.

Prolonged exposure to anesthetics can lead to neuroapoptosis and neurocognitive problems. However, other studies suggest that even low nonapoptotic concentrations of general anesthetics may inhibit normal synapse formation and damage developing neuronal networks. Mechanisms underlying neurodevelopmental toxicity are potentially linked to the same ion channels hypothesized to mediate general anesthesia. General anesthetic actions are attributed in part to both antagonism of *N*-methyl-d-aspartate receptor and potentiation of GABA-A receptor signal transduction, and drugs with either or both of these activities damage developing brains.

### ***POST OPERATIVE DELIRIUM-***

American Psychiatric Association defines delirium as an acute change in cognition or disturbance of consciousness that cannot be attributed to a pre-existing medical condition, substance intoxication or medication. However various conditions such as age, functional status and substance abuse influence the risk of immediate and post operative delirium. Delirium in the

postoperative period can be divided into emergence delirium and post operative delirium depending on the time of presentation. Emergence delirium or emergence agitation is usually observed immediately after GA and is related to anesthetic drugs. It is common in children with peak age being 2-4 years. It is accompanied by psychomotor agitation which includes a series of unintentional and purposeless motion like pacing around a room, wringing ones hands, pulling off clothing, and self-extubation. It usually occurs within the first 10 minutes of recovery and resolves within minutes to hours without long term neurological effects. It is more commonly associated with less soluble inhalational anaesthetics like sevoflurane and desflurane.

Postoperative Delirium(POD) usually presents 24-72 hours following a lucid interval. It usually resolves within hours to days. Post operative delirium can have lasting effects beyond the perioperative period. POD has also been associated with postoperative depression, posttraumatic stress disorder-like syndrome which may impede recovery. As a result, delirium may have long-term mental health complications.

POD has been previously reported to occur following several kinds of surgery, including general surgery , head and neck cancer surgery, cardiac surgery , vascular surgery , hip fracture and joint replacement surgery.The incidence of post operative delirium(POD) in various studies ranges from 5% to 15%.Within certain high-risk groups such as hip fracture patients, the range is 16–62% with an average of 35%. The incidence of POD in spine surgery in previous studies was found to be between 3.3% to 3.8%.

### ***RISK FACTORS FOR POSTOPERATIVE DELIRIUM-***

The mechanism of postoperative delirium is not clear. However ,studies have shown that major risk factors include age >70 years, pre-existing cognitive impairment, preoperative use of narcotics

or benzodiazepines, previous history of POD, alcohol abuse, breast and abdominal surgeries, long duration of surgery and preoperative cognitive dysfunction. Precipitating factors include: the use of physical restraints, malnutrition, the use of a urinary bladder catheter and electrolyte and fluid abnormalities. Specific perioperative risk factors include greater intraoperative blood loss, more postoperative transfusions, and postoperative haematocrit of <30%.

Severe acute pain regardless of the method of analgesia (opioid type, method and dose) is associated with POD. Certain types of injury, particularly hip fractures, and serious illness requiring intensive care are also associated with a high incidence of delirium^2. Several factors with positive correlation with POD may also suggest an association with preoperative anxiety.

Incidence of POD was greater with inhalational anesthetic agents than with propofol. Other risk factors of delirium include vision impairment, severe illness, cognitive impairment, and serum urea nitrogen: creatinine ratio of 18 or greater, vascular risk factors (tobacco use and vascular surgery), decreased cerebral perfusion, low preoperative executive scores and depressive symptoms, pre-existing attentional deficits in non-demented patients. Previous history of illness and long term treatment with antidepressants were associated with a decreased risk for POD.

### ***PHARMACOLOGY OF ISOFLURANE-***

Isoflurane is a volatile anaesthetic agent. Chemically it is 2-chloro-2-(difluoromethoxy)-1,1,1-trifluoro-ethane. It has a boiling point of 48.5 degree Celsius and a vapour pressure of 238 mm Hg. The blood /gas partition coefficient of isoflurane is 1.4 at 37 degree Celsius and MAC – immobility is 1.28 mm Hg. At concentrations greater than 1 MAC, isoflurane increases CBF and intracranial

pressure. Isoflurane reduces cerebral metabolic oxygen requirements, and at 2 MAC, it produces an electrically silent electroencephalogram(EEG).

Many animal studies have demonstrated the neurotoxic effects of isoflurane-

Studies have demonstrated that there was increased apoptotic cellular degeneration and neurodegeneration following isoflurane exposure in neonatal mice and rhesus monkeys.Liu J. et al demonstrated that in young adult mice, isoflurane may cause neurotoxicity by inducing caspase activation and apoptosis with the anesthetic concentration increased and duration prolonged. High concentration of isoflurane exceeding 4 hours may induce a decline of NR2B and ratio of pERK1/2 to ERK1/2 resulting in cognitive impairment.

There are studies which have also demonstrated neuroprotective effects of isoflurane. Liu J. et al demonstrated that in young adult mice ,low concentration of isoflurane in 2 hours can induce a hippocampus-specific elevation of NR2B subunit composition and ratio of p-ERK1/2 to total ERK1/2,thereby producing hippocampal-dependent cognitive improvement.Engelhard K et al demonstrated that desflurane and isoflurane improve neurological outcome after incomplete cerebral ischaemia in rats.Milner E et al demonstrated improved neurological outcome in subarachnoid haemorrhage in mice with isoflurane.

### ***PHARMACOLOGY OF DESFLURANE-***

Desflurane ,a volatile anesthetic agent was introduced into clinical practice in 1992. Chemically it is fluorinated methyl ethyl ether. Two most important physical properties of desflurane are that it has a boiling point of 22.8C and a vapour pressure of 664 mmHg. So it boils at room temperature and hence a special vaporizer is required to deliver desflurane. It has a blood/gas partition coefficient of 0.45 at 37 degree Celsius which is the least among the inhalational agents and a MAC- immobility of 6.0 mmHg. This favors rapid achievement of alveolar concentration

necessary for production of anesthesia followed by rapid recovery on discontinuation. This anesthetic property makes it a favourable anesthetic agent for neurosurgery.

Central nervous system (CNS) actions: Desflurane decreases cerebral metabolic rate (CMR) by 35%. Cerebral blood flow (CBF) may increase or decrease depending on concentration used. At 1 minimum alveolar concentration (MAC), desflurane decreased  $CMRO_2$  by 50%, CBF by 22% and at the same time cerebrovascular reactivity is preserved. Desflurane has been found to be neuroprotective in certain animal studies. The mechanism of neuroprotection involves reduction of glutamate, potentiation of GABA receptors, regulation of intracellular calcium responses and activation of potassium channels. However it may raise ICP more than isoflurane, hence it should be used cautiously in patients with unstable ICP.

### **AIMS OF THE STUDY-**

- 1)To compare the incidence of postoperative delirium with isoflurane and desflurane on adults undergoing spine surgery .
- 2)To determine the perioperative factors which can influence postoperative delirium.

## **MATERIALS AND METHODS**

The proposed study will be a prospective randomized clinical trial. It will be carried out for a period of 15 months from January 2016 to June 2017 in 60 adult patients scheduled for spine surgery at PGIMER, Chandigarh. Ethical clearance will be sought from the human and ethics committee of the institute. Written informed consent will be taken from all the patients. The patients will be randomly divided into two groups of 30 each - Group I (Isoflurane) and Group D (Desflurane) prior to surgery.

### **Selection of patients-**

#### ***Inclusion criteria***

- Patients scheduled for spine surgery.
- Age between 18-65 years
- American Society of Anaesthesiologists (ASA) Grade I and II patients
- Patients with Glasgow Coma Scale (GCS) of 15
- Postoperative Aldrette score > 9

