#### ***Exclusion criteria***

- Cardiorespiratory disorders
- Associated cerebral disease
- Psychiatric illness
- Electrolyte and hormonal imbalance
- History of drug abuse

- Postoperative meningitis
- Administration of high dose steroids

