### **Randomization and blinding**

Randomization will be done using computer-generated random numbers. The patient will be randomized to receive isoflurane or desflurane anaesthesia prior to surgery. All the patients involved in the study will be blinded to group allocation. The physician administering anaesthesia will be presented with envelopes containing the random numbers with the assigned groups just prior to surgery. The investigator will be blinded to group allocation.

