### **Anaesthesia Protocol**

All the preoperative medications will be continued on the day of surgery. Anaesthesia will be induced with propofol 2-2.5 mg/kg and fentanyl 2 ug/kg. Vecuronium 0.1 mg/kg will be used to facilitate endotracheal intubation. All the patients will be monitored with 5 lead electrocardiogram, pulse oximeter, non-invasive blood pressure, temperature, airway gas levels, end-tidal carbon-dioxide concentration and urine output. Maintenance of anaesthesia will be carried out with either isoflurane or desflurane as per the randomization. The depth of anaesthesia will be monitored using entropy (to keep state entropy between 40 and 60). Analgesia will be maintained with fentanyl 0.5-2 ug/kg/hour and Vecuronium 0.06 mg/kg will be used intermittently for neuromuscular blockade to maintain less than two twitch response on neuromuscular transmission (NMT) monitoring. Replacement fluid will consist of normal saline. Intraoperative haemodynamics, oxygen saturation, temperature and blood loss will be recorded and compared among the two groups. The patients will be administered an antiemetic intraoperatively. At the end of the procedure neuromuscular blockade will be antagonized with neostigmine (0.05mg/kg)

and glycopyrrolate (0.01mg/kg). The patients who cannot be extubated at the end of the procedure will followed up in the postoperative period. The patients who cannot be extubated within forty-eight hours following surgery will be excluded from the study.

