## STATISTICAL ANALYSIS

All analysis will be done using SPSS version 22 (SPSS Inc., Chicago, IL, version 16.0 for Windows). Descriptive statistics will be obtained for demographic patient related and treatment related variables. The variance between both the treatment groups will be analysed using two way ANOVA. The primary end points will be compared between the two groups using chi square statistics. As a secondary outcome measure, univariate and multivariate analysis will be done to identify the factors that may influence post operative delirium.

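### Patients are randomised before surgery but can be removed on postoperative events, and no analysis population is named for the primary chi-square test

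*Combined protocol and SAP*

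**What the plan says.** All references are to the combined protocol and SAP.

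- **Allocation.** Materials and Methods: "The patients will be randomly divided into two groups of 30 each". Randomization and blinding: "The patient will be randomized to receive isoflurane or desflurane anaesthesia prior to surgery". The preoperative workup list also places assignment of the random number before surgery.
- **Recovery score.** The inclusion criteria contain "Postoperative Aldrette score > 9", with no time of measurement.
- **Extubation.** The Anaesthesia Protocol says "The patients who cannot be extubated at the end of the procedure will followed up in the postoperative period", and then "The patients who cannot be extubated within forty-eight hours following surgery will be excluded from the study".
- **Other exclusions.** The exclusion criteria contain "Postoperative meningitis" and "Administration of high dose steroids". The steroid item has neither a time nor a threshold.
- **Analysis.** Statistical Analysis says "The primary end points will be compared between the two groups using chi square statistics". Neither that section nor the sample size text names an analysis population, a rule for patients removed after randomisation, or a rule for missing outcomes. No other section supplies them.

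**The concern.** Randomisation makes the two groups comparable at allocation. Two rules certainly act later: failure to extubate within 48 hours, and postoperative meningitis. A third, the Aldrete item, can only be known after surgery, but its role is unclear. It may be an eligibility filter, or only a check that the 3D-CAM can be given. The fourth, high-dose steroids, may refer to use before or after allocation.

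With no analysis population stated, following these rules literally drops randomised patients because of events after the study agent was given. The Introduction says desflurane gives faster emergence than isoflurane, so a filter based on recovery could remove different numbers by arm. If the removed patients also differ in delirium risk, part of the observed difference would come from selection and not from the agent.

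**Working it through.** **1. The plan's own figure.** Inputs from the sample size text: 27% and 0%, margin 5 points, alpha 0.05, power 85%. With unpooled variance and one-sided alpha (sidedness is not stated), n per arm = 0.27 × 0.73 × (1.645 + 1.036)² / (0.27 − 0 − 0.05)² = 29.28. This rounds up to 30 per arm, or 60 in total, and matches the plan. No reserve for removals is stated. On the same formula, power is 85.8% at 30 per arm, 82.4% at 27 and 78.3% at 24.

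**2. Timing of each rule against allocation**

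| Rule | Acts after allocation? |
|---|---|
| Not extubated within 48 h | Yes |
| Postoperative meningitis | Yes |
| Postoperative Aldrete score | Measured after surgery; time and role not stated |
| High-dose steroids | Not stated |

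The Aldrete item also sits uneasily with the Anaesthesia Protocol. If it is read at the end of surgery as an eligibility rule, it may remove the patients whom that section follows up because they could not yet be extubated.

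**3. Possible size of the selection effect.** Assume no true difference. Let p be the delirium risk in each arm, e the fraction excluded, and k the risk in excluded patients relative to retained ones. Then retained risk = p / (1 − e + e·k). The documents give p = 3.3–3.8% for spine surgery; e and k are assumptions. The small case excludes 1/30 in one arm and none in the other. The large case excludes 20% and 5%.

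Example, p = 3.8%, large case, k = 3: 0.038/1.40 = 2.71% and 0.038/1.10 = 3.45%, a spurious difference of 0.74 points.

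| p | Case | Difference in points, k = 2 and k = 3 | False-positive rate, k = 2 and k = 3 | With no exclusion |
|---|---|---|---|---|
| 3.3% | small | 0.11, 0.21 | 1.13%, 1.10% | 1.23% |
| 3.3% | large | 0.39, 0.64 | 0.77%, 0.58% | 1.23% |
| 3.8% | small | 0.12, 0.24 | 1.56%, 1.53% | 1.69% |
| 3.8% | large | 0.45, 0.74 | 1.0%, 0.81% | 1.69% |
| 27% | small | 0.87, 1.69 | 5.10%, 5.27% | 4.92% |
| 27% | large | 3.21, 5.26 | 5.80%, 7.23% | 4.92% |

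False-positive rates are by exact enumeration: 30 per arm randomised, binomial exclusion, uncorrected chi-square at two-sided 0.05. The 27% rows are an upper illustration only. That figure is a rate of postoperative cognitive dysfunction in one arm of a study with 15 patients per group, not a delirium rate. With equal exclusion in both arms, or k = 1, the bias is zero.

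**4. Sensitivity to one patient.** At 3.8%, 30 × 0.038 = 1.1 delirium cases are expected per arm. Illustrative tables, uncorrected chi-square: 4/30 v 0/30 gives p = 0.038, and removing one delirious patient (3/29 v 0/30) gives 0.071. In the other direction, 6/30 v 2/30 gives 0.129, and 6/30 v 1/29 gives 0.049.

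**5. Which rule for patients with one assessment.** Assume the outcome is delirium on either day. Let u be the fraction with one assessment and d the chance that a delirious patient is positive at it (assumed 0.5 to 1), with p = 3.8%.

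- A negative requires both assessments: rate = [p(1 − u) + p·u·d] / [(1 − u) + p·u·d]. With u = 20% v 5% and no true difference, this gives 4.25% v 3.90% (d = 0.5) and 4.71% v 3.99% (d = 1), a spurious 0.36 to 0.71 points.
- Available assessments are used: rate = p(1 − u) + p·u·d. This gives 3.42% v 3.71% (d = 0.5) and 3.8% v 3.8% (d = 1), a spurious 0.29 to 0 points.

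The first rule creates about as much bias as the large case in step 3, and it still drops patients because of late extubation. The second is the better primary rule.

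**The case against.** The strongest reply is that little harm is shown. The documents give no exclusion rates. They do not link the agent to the Aldrete score, to extubation at 48 hours, to meningitis or to steroid use; speed of emergence is the only stated link. The patients are ASA I–II, and no frequency is given for extubation failure. The Aldrete item may only mark whether a question-based test can be given, and the steroid item may be a baseline exclusion. The investigator is blinded to allocation. At the documents' own delirium rate the calculated shift is under one point and the false-positive rate falls slightly.

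Most of this stands, and it limits how much weight the point can carry. It does not close the gap. Blinding the investigator limits discretionary removal by that person, but not removal driven by the agent, nor decisions by the anaesthetist, who knows the allocation. Two removal rules act after allocation on any reading, and nothing says that these patients stay in the analysis.

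A reader might infer that all four rules act after allocation, or that the chi-square test will be run on the reduced set. The text supports neither. Two rules are ambiguous, and the analysis section is silent.

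**Conclusion.** The gap is clear from the text: the primary comparison, as written, need not be between the randomised groups. Confidence is high on that, and not on material bias. Under the assumed exclusion rates and risk ratios, the shift at 3.3–3.8% is about 0.1 to 0.7 points, with no rise in false positives. The true size and direction cannot be determined.

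A reader might go further and infer that the plan inflates the type I error or favours one agent. Marked inflation can be produced: at a 15–27% delirium rate, removing half of the delirious patients in one arm only gives 12.6–17.5%. That assumes heavy, one-sided removal of the delirious patients themselves, at rates well above those the documents quote for spine surgery. Nothing in the documents supports it. The case for change is that stated rules break the randomised comparison, events will be few, and the correction is cheap.

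**What to change.** 1. In Statistical Analysis, add: *All randomised patients will be analysed in the group to which they were allocated. No patient will be removed from the analysis for an event after randomisation (Aldrete score, extubation time, meningitis, or steroids given after allocation).*
2. Reconcile the Aldrete criterion with the follow-up and 48-hour statements in the Anaesthesia Protocol. State when the score is measured and whether it only records that the 3D-CAM can be given at a visit. State whether the steroid exclusion is judged before allocation.
3. In the primary comparison, use every randomised patient with at least one 3D-CAM assessment, on the assessments available. Treat patients with none as missing. Run two sensitivity analyses on all 60: missing counted as delirious in one arm and not in the other, then the reverse. Add a further one that treats single negative assessments as missing.
4. Report post-randomisation events, untestable visits and single-assessment patients by arm, with reasons.

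The cost is protocol wording and three sensitivity analyses. The sample size stays at 60 and clinical care does not change. There are two downsides. Patients with no assessment still leave the primary comparison, and each moves the bounding difference by 1/30 = 3.3 points. A single negative assessment may also miss some delirium: with 10% single-assessed (assumed), a true 3.8% reads as 3.61–3.80%.
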